## 1 BACKGROUND

**Adherence challenges in YMSM threaten to compromise PrEP's effectiveness.** Men who have sex with men (MSM) are the only risk group in the U.S. who have not experienced decreased HIV incidence, with increasing incidence specifically demonstrated among young MSM (YMSM). PrEP with adequate adherence is highly effective, both at the individual and population level. A recent analysis demonstrates that, among sexually active US MSM, the proportion eligible for PrEP has jumped from 24.7% in 2015 to 45% today with an update in practice guidelines. Indeed, rising numbers of U.S. MSM have initiated PrEP, with up to 50% of MSM having tried PrEP in the prior year in some districts, including San Francisco. PrEP expansion is a critical component of the newly-launched End the HIV Epidemic campaign in the U.S. However, poor adherence can compromise PrEP's effectiveness in the populations at greatest risk. Data from two U.S. PrEP demonstration projects has shown that up to 66-78% of YMSM exhibit low PrEP adherence. Furthermore, a drop-off in adherence may herald future PrEP discontinuation, meaning that new non-adherence may be a critical period for intervention in individuals who remain at risk. Although some stop PrEP due to decreasing HIV risk, many who stop PrEP remain at risk of HIV: in a Montreal clinic, the HIV incidence after stopping PrEP was as high as the placebo arm of the iPrEx trial.

**Objective adherence monitoring effectively identifies adherence challenges.**

Pharmacologic metrics of adherence, where drug levels are measured in a biomatrix such as dried blood spots, plasma or hair, predict the efficacy of PrEP better than other measures such as self-reported adherence. The low correlation between self-report and pharmacologic metrics was seen not just in randomized trials, but also in open label studies after the efficacy of PrEP was known. Among YMSM in particular, the U.S. demonstration projects for young and adolescent MSM (Adolescent Trials Network (ATN) studies) demonstrated that self-reported adherence and electronic pill-cap monitoring (via Wisepill) both had low correlation and accuracy when compared to pharmacologic measures of adherence (drug levels in hair and dried blood spots, DBS), echoing findings in other populations. As a result, pharmacologic metrics of adherence are now often included in PrEP roll-out projects and demonstration studies to aid in outcome interpretation.

**Point-of-care (POC) urine adherence screening is now feasible and scalable.**

Previously available methods to measure drug levels for pharmacologic monitoring, no matter which biomatrix tested, required expensive spectrometry-based equipment, usually liquid chromatography/tandem mass spectrometry (LC-MS/MS) machines. Moreover, LC-MS/MS-based methods require long turn-around times and personnel with specialized training. A point-of-care (POC) method to measure drug levels in urine using a low-cost (<\$2), easy-to-perform, rapid turnaround (<2 minutes) antibody-based assay has recently been developed for tenofovir disoproxil fumarate/emtricitabine (TDF/FTC)-based PrEP. Urine collection is noninvasive and preferred among youth over blood sampling. Furthermore, POC adherence monitoring could be performed on urine specimens already collected for gonorrhea and chlamydia infection STI screening as part of routine PrEP care for MSM, requiring few changes in procedures and minimal time to implement in clinical settings.

**Monitoring and feedback on adherence metrics or clinical outcomes can be used to enhance adherence counseling across multiple disease states.** Patients adhere to life-saving cardiovascular and diabetes medications approximately 50% of the time.

Monitoring and feedback of disease outcomes is used to motivate adherence across prevention and treatment of a variety of disease states, such as prediabetes/ diabetes, prehypertension/hypertension, obesity, and heart failure (hemoglobin A1c and glucose; blood pressure recordings; weight; remote pulmonary artery pressure monitoring respectively). Furthermore, objective adherence monitoring is now performed for several conditions; examples include urine drug-level testing for anti-hypertensive medications in resistant hypertension, leading to subsequent improvements in medication adherence and blood pressure, and remote monitoring of insulin delivery and carbohydrate entry with insulin infusion pumps among adolescents with type 1 diabetes, leading to improved adherence and glycemic control. Finally, studies have utilized objective adherence monitoring, including drug-level measurement, to enhance motivational interviewing-based adherence counseling to improve adherence in severe mental illness, substance use, asthma, obstructive sleep apnea, and HIV treatment.

**Real-time adherence feedback, contextualized through counseling, can be used to interpret and motivate adherence to PrEP.** In the iPrEx-Open Label Extension (OLE) study conducted among MSM and transwomen, plasma TFV levels were analyzed and feedback was provided at a later visit. Many with low adherence noted that feedback encouraged them to improve their adherence, while those with high adherence felt that the result motivated them to maintain their adherence. However, participants reported that adherence feedback would have less impact on their behavior without contextualization through counseling. A demonstration project in Los Angeles MSM therefore included MI-based counseling with plasma TFV-level feedback. The study demonstrated high acceptability, with a trend towards improved adherence among those who received their drug-levels. MSM found drug-level feedback with MI-based counseling highly acceptable, particularly when contextualized as “level of HIV protection,” with participants competing to achieve the highest drug level result. Finally in HPTN 082, a study of drug-level feedback using lab-based TFV-diphosphate monitoring in DBS among young African women on PrEP, long delays in receiving results limited acceptability, with the investigators recommending use of POC drug level testing in future studies. Based on the evidence available, (1) drug-level feedback should be supported by counseling to contextualize results and motivate improved adherence; and (2) drug-level feedback should be provided as close as possible to the visit before recall of recent adherence and motivation waned. However, POC objective adherence metrics have not been available until now.

**A POC bioassay-enhanced PrEP adherence brief intervention is promising and feasible for busy clinical settings.** Motivational interviewing (MI)-based techniques to improve medication adherence are effective and have been embraced by primary care and HIV providers for prevention and treatment of chronic conditions. Brief interventions are structured MI-based strategies most widely used for substance use interventions, but have since been adapted to interventions to improve medication adherence. To our knowledge, brief interventions have not yet been adapted to PrEP use. These brief interventions have 3 basic steps (1) screen for adherence challenges and provide adherence feedback, (2) enhance motivation, and (3) strategize and jointly set goals to improve

adherence. Due to their efficacy, simplicity to learn and teach, and ability to be performed in short clinical encounters, brief interventions have received widespread uptake among primary care providers. Brief interventions have been adapted for use with adherence monitoring (step 1 above) using the metrics of self-reported adherence and electronic pill-cap monitoring systems. However, given greater accuracy of therapeutic drug monitoring (TDM) to monitor PrEP adherence and the predictive ability of TDM to identify individuals at risk of HIV due to low adherence, a brief intervention triggered and informed by a POC adherence metric could both improve adherence and prevent HIV infections.

**Preliminary Data:** Below, I present preliminary data on (1) adherence in YMSM at SFCC; (2) validation of the urine POC immunoassay; (3) barriers to adherence reported by SFDPH PrEP users and medical providers; and (4) a conceptual model of PrEP adherence and proposed mechanisms of behavior change via PrEP-BAY.

**YMSM have adherence challenges and a drop-off in adherence heralds future PrEP discontinuation.** In an analysis of data from the U.S. PrEP Demonstration Project, conducted between October 2012 and February 2015, for which SFCC was the largest site, we examined short-term adherence to PrEP using emtricitabine-triphosphate (FTC-TP) levels in dried blood spots (DBS). FTC-TP assesses adherence in the prior week similar to urine tenofovir (TFV) measurement. We found that 25% of participants had undetectable FTC-TP levels over the study duration, and a drop-off in short-term adherence heralded future PrEP discontinuation (adjusted hazard ratio: 6.3; 95% Confidence Interval (CI): 3.8-10.2). FTC-TP levels predicted future discontinuation more strongly than long-term adherence metrics (e.g. TFV-diphosphate levels in DBS). Younger (age<30) vs. older MSM had 2.5-fold higher odds of low FTC-TP (95% CI: 1.7-3.9).

**The POC urine immunoassay is sensitive, specific, and highly correlated with gold-standard metrics; low adherence via the assay identified MSM at risk of future HIV seroconversion.** Samples from a directly observed therapy (DOT) study (n=30), where

standard, LC-MS/MS (R01 AI143340 PI: [name]). The novel immunoassay was sensitive (94%), specific (99%), and the correlation was high (0.92,  $p < 0.001$ ). A cut-off of 1,500 ng/ml accurately classified 98% of patients who took a dose within the last 24 hours as adherent. The immunoassay has now been developed, validated against LC-MS/MS concentrations with high sensitivity and specificity, and packaged into a POC test with this cut-off (**Fig. 1**). Finally, in a secondary data analysis of a large PrEP demonstration project, the iPrEx-OLE study, we found that low vs. high urine TFV was associated with 14-fold higher odds of future HIV seroconversion (95% CI: 1.3-1197).

TDF/FTC was given to HIV-uninfected volunteers at 2, 4 and 7 doses per week, were used to compare urine TFV levels by the novel immunoassay with levels derived from the analytic gold

**Barriers to PrEP adherence in YMSM could be amenable to counseling; drug-level feedback can further enhance adherence counseling.** To assess barriers to non-adherence that could potentially be amenable to counseling, we analyzed preliminary data

from the PrEP Persistence Study (R01 MH109320 PI [name]) using the situated-Information-Motivation-Behavioral Skills model (sIMB). The PrEP Persistence study performed in-depth interviews among 28 PrEP users (50% age<30) and 18 PrEP providers to assess barriers and facilitators of PrEP persistence (continued PrEP use over time).

YMSM, in particular, reported that (1)

additional *information* about addressing missed doses and adherence necessary for protection would be helpful; (2) they experienced difficulty finding *motivation* for daily pill-taking in the context of other obligations and stressors; and (3) they were “taking a daily medication for the first time,” and thereby, could have used additional support in developing a pill-taking routine. In a presentation of preliminary data regarding the POC adherence test to the SFDPH Bridge HIV community advisory group (CAG), members felt that

drug-level feedback would enrich adherence counseling if delivered supportively. One CAG member stated, “It shows my doctor values my protection [from HIV] so much that they are double-checking that the medication is in my body” (Fig. 2).

**Fig. 2: Themes and illustrative quotes from preliminary data**

**Developing motivation for adherence is a challenge**

[figure not shown]
“Remembering to take the pill, on top of work, school, you know, it sometimes feels like a lot and I’m trying to stay...motivated” (age 19)

**Behavioral skills support PrEP adherence**

“I got into a routine, so I knew I was consciously doing it. I would put one in my coin pocket so that I had one on me...like a backup plan” (age 27)

**Drug-level feedback, if real-time, is motivating**

**Fig. 3: Adapted situated Information Motivation Behavioral Skills (sIMB) Model for PrEP Adherence and how PrEP-BAY could address these factors**

1. Bold indicates proposed aspects of the model that will require additional testing in Aims 1 & 2.

**We have developed a preliminary conceptual model of PrEP adherence among YMSM.** Guided by factors in our preliminary data and literature review, our conceptual model (Fig. 3) is based on the situated Information-Motivation-Behavioral Skills model (sIMB; previously applied to HIV therapy and more recently to PrEP adherence among MSM and YMSM). We posit that the PrEP-BAY intervention (presented in the yellow box) can foster pill-taking by enhancing adherence information (via drug-level feedback and discussion of timing of HIV protection based on adherence); motivation (through MI components including: (1) assessing readiness for behavioral change; (2) discussing sources of support and restating motivation to improve); and behavioral skills (setting a

joint follow-up plan, specifying a reminder, cueing, or strategy, and agreeing on a follow-up time with the provider by phone or in-person).

In summary, preliminary data reveal the need for additional PrEP adherence support among YMSM. In addition to receiving support for psychosocial challenges, YMSM report that interventions which enhance motivation to take PrEP and encourage the development of pill-taking strategies, which is the focus of PrEP-BAY, are likely to be successful. Prior studies of drug-level feedback to support adherence reveal a need to (1) contextualize results and motivate improvement with counseling and (2) provide information on drug levels in real-time.

## 2 STUDY RATIONALE

There are three important aspects that support the implementation of this pilot randomized controlled trial: (1) we will assess implementation of the first POC metric for assessing PrEP adherence objectively among MSM for the first time; (2) we will develop the first brief intervention for PrEP adherence; and (3) we will develop adherence support tailored specifically for YMSM, a population with rising HIV incidence in the U.S.

**1. We will use the first POC objective adherence assessment to support PrEP adherence among YMSM.** Although pharmacologic metrics of adherence have been previously used to enhance and target adherence counseling, no clinically-validated POC metric for PrEP adherence has existed until now. This novel easy-to-perform POC urine assay will permit drug-level adherence feedback to be delivered in the context of routine PrEP clinical visits by the patient's clinician, before memory and motivation to improve on recent adherence patterns has waned. This approach has the potential to be adapted to other PrEP strategies, such as tenofovir alafenamide (TAF), as well as to HIV treatment and the management of other chronic diseases.

**2. We will adapt an adherence screening and brief intervention to PrEP.** This study will adapt an MI-based brief intervention widely used in primary care settings for other disease states for use in PrEP. Brief interventions have been effective in other contexts to support medication adherence and have high uptake among primary care providers. Given that brief interventions are simple to learn and quick to perform, they have the potential for scalability and adoption across a variety of primary care and sexual health clinic settings. However, to our knowledge, no brief intervention has yet been developed for PrEP adherence.

**3. We will develop an adherence tool specifically tailored for YMSM.** YMSM are a population with rising HIV incidence. YMSM have unique medical and sexual health needs in the context of negotiating independence from caregivers, exploring sexual identity, and if interested in PrEP, often taking a medication for the first time. We will develop a counselling tool specifically developed for YMSM's sexual health needs and goals and enroll YMSM ages 18 and older to fully explore the tool among adolescents.

### 3 STUDY OBJECTIVES

#### 3.1 Primary Objective

The primary objective is to assess the acceptability of the PrEP2-BAY intervention over a three-month period, implemented over two counseling sessions in concert with PrEP adherence feedback among YMSM using PrEP.

#### 3.2 Secondary Objectives

The secondary objective is to assess the impact of the PrEP2-BAY intervention on long-term PrEP adherence (using tenofovir levels in hair) over a three-month period.

### 4 STUDY DESIGN

#### 4.1 Study Overview

We will conduct a 3-month pilot study of the PrEP2-BAY intervention to assess its accessibility and the preliminary impact on adherence. Participants will be randomized 2:1 to the additional PrEP2-BAY adherence intervention vs. continued standard of care at their PrEP clinic. We will assess the acceptability of the intervention through surveys and interviews. Finally, we will assess preliminary impact on long-term adherence through measurement of tenofovir levels in hair compared from baseline to month 3 across study arms.

### 5 CRITERIA FOR EVALUATION

#### 5.1 Primary Endpoint

Acceptability will be the primary outcome for this pilot randomized controlled trial, and will be assessed via tabulation of survey results with graded answers in the intervention arm. We will use a threshold of  $\geq 75\%$  reporting that they were at least somewhat satisfied with the full PrEP2-BAY intervention. After analysis of the quantitative results, we will explore mechanisms of acceptability using a sequential explanatory mixed methods approach.

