STUDY DESIGN	This is a randomized, unblinded, open-label pilot study

PRIMARY OBJECTIVE	To test the acceptability to participants and impact on a longer-term metric of adherence among participants (assessed via tenofovir levels in hair) of implementing POC urine tenofovir testing and providing adherence feedback and motivational interview-based counseling among YMSM in the U.S.
NUMBER OF SUBJECTS	60 participants, 40 in the intervention arm and 20 in the standard-of-care arm
SUBJECT SELECTION CRITERIA	
Inclusion Criteria:
 
 
1. Age 18-30 years.
 
2. Primary sexual partners are male sex at birth
 
3. Able to understand, read, and speak English.
 
4. Currently taking TDF/FTC-based, daily PrEP and planning to continue for at least 3 months
 
5. Willing to provide a hair sample
 
 
Exclusion Criteria:
 
 
1. Any health condition that may interfere with participation or the ability to provide informed consent, including any debilitating or life-threatening conditions
 
2. Currently enrolled in another HIV intervention study.
 
3. Known to be HIV-infected.
 

POC TESTING	Urine tenofovir testing by lateral flow assay performed at each of 2 counseling sessions approximately 2-3 months apart
CONTROL	Participants will continue to receive standard of care at their PrEP clinic without the PrEP2-BAY adherence counseling intervention
DURATION OF SUBJECT PARTICIPATION AND DURATION OF STUDY	Participants will be enrolled in the study for a maximum of 3 months, including the enrollment period and 3 months of study follow-up.
PRIMARY ENDPOINT	
 
• Acceptability: Number of participants indicating satisfied or very satisfied with the intervention
 
• Description: Number of participants reporting to be "satisfied" or "very satisfied" about their overall experience on a five-point Likert scale.
 
• Time Frame: 3 months
 

SECONDARY ENDPOINTS	
 
• Change in tenofovir levels in hair from baseline and after 3 months of follow-up
 

PLANNED INTERIM ANALYSES	When approximately 50% of patients have completed all study procedures, an interim analysis of all data will be conducted by an

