Rationale for Number of Subjects	We will assess sample size based on the primary endpoint of acceptability, with a threshold of $\geq 75\%$ reporting that they were at least somewhat satisfied with the full PrEP2-BAY counseling intervention. We will base our estimate of acceptability on a similar intervention performed among Los Angeles MSM (PATH-PrEP),  which was $\sim > 90\%$ acceptable. Using an estimate of PrEP2-BAY being somewhat acceptable for 90% of the 40 individuals in the intervention

	arm, we would have 82% power to detect acceptability of 75% or less with a one-sided alpha of 0.015.
--	--

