## 10.2 Statistical Analysis

Acceptability, the primary outcome, will be assessed through tabulation of survey results and in-depth interviews. We will use a threshold of  $\geq 75\%$  reporting that the full PrEP-BAY intervention was at least somewhat acceptable on a 5-point Likert scale, and then explore potential mechanisms through in-depth interviews using a sequential explanatory mixed methods approach. For the interviews, we will analyze transcripts using the codebook and theoretical model developed in Aim 2, applying it to a subset of transcripts. We will seek 90% agreement among coders prior to applying codes to the entire set of interviews. We will use code reports to organize findings into emergent themes and discuss these as a group and with the HIV prevention community advisory group.

Preliminary impact (adherence) will be assessed via a long-term adherence metric, namely DBS TFV-DP levels. We will use mixed effects logistic regression for high adherence (at least 4 times weekly dosing; TFV-DP  $\geq 700$  fmol/punch) comparing the interaction of adherence by intervention arm with time. Random intercepts will accommodate paired adherence levels. As an additional adherence outcome, we will examine continuous DBS TFV-DP levels using censored mixed-effects linear regression in a similar fashion.

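### The 75% acceptability threshold does not have the 82% power and one-sided alpha of 0.015 used to justify 40 intervention participants

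*Combined protocol and SAP*

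**What the plan says.** Section 5.1 states that acceptability "will be assessed via tabulation of survey results with graded answers in the intervention arm. We will use a threshold of" at least 75% "reporting that they were at least somewhat satisfied with the full PrEP2-BAY intervention". The synopsis (Statistics, Primary Analysis Plan) uses the same threshold and adds frequency distributions of the Likert scale. Section 10.2 reads: "Acceptability, the primary outcome, will be assessed through tabulation of survey results and in-depth interviews", again with 75% as the mark. None of the three gives a hypothesis test, a confidence interval, an alpha or a count that would meet the threshold.

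The synopsis sets the size as "60 participants, 40 in the intervention arm and 20 in the standard-of-care arm". Its Rationale for Number of Subjects assumes a true rate of 90% among those 40 and states: "we would have 82% power to detect acceptability of 75% or less", at a one-sided alpha of 0.015. No section says that this one-sided comparison will be carried out.

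On missing ratings the plan is silent. The synopsis gives the endpoint a 3-month time frame, and section 9.7 allows withdrawal at any time.

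**The concern.** The sample size rests on a one-sided comparison with 75% at a small alpha. The analysis text compares an observed percentage with 75%. An observed proportion equal to the reference value cannot show that the true proportion exceeds it, so the two procedures cannot share error rates. This is the only primary endpoint and the only basis given for the sample size. A reader of the results could take a pass at 75% as carrying the quoted 1.5% error. If the rule is settled only after the data are seen, the conclusion for a result in the low to mid 30s out of 40 will depend on which part of the plan is followed.

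**Working it through.** **Inputs.** n = 40 in the intervention arm (synopsis, Number of Subjects). Threshold 75% (section 5.1, section 10.2, synopsis). Assumed true rate 90%, reference rate 75%, one-sided alpha 0.015, power 82% (synopsis, Rationale for Number of Subjects).

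**1. The plan's own figure.** Take 75% as the reference, 90% as the truth, and the variance at 90%:

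- Standard error = √(0.90 × 0.10 / 40) = 0.0474.
- (0.90 − 0.75) / 0.0474 = 3.162, and z for 0.985 = 2.170.
- Power = Φ(3.162 − 2.170) = Φ(0.992) = 83.9%. The one-sample t version (noncentral t) gives 81.5%.

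So 82% is reproduced to within 2 points, but only with the variance taken at 90%. At the same alpha, other methods give less: null-variance test 51%, arcsine 65%, exact binomial 42% (37 of 40 needed). With the direction reversed (90% as reference, 75% as truth) the result is 75% by the normal approximation and 56% exactly.

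**2. The rule in the analysis text.** An observed proportion of at least 75% is at least 0.75 × 40 = 30 of 40. With X binomial(40, p), P(pass) = Σ C(40, x) pˣ (1 − p)⁴⁰⁻ˣ for x = 30 to 40:

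| True rate p | P(at least 30 of 40) |
|---|---|
| 0.65 | 0.12 |
| 0.70 | 0.309 |
| 0.75 | 0.584 |
| 0.90 | 0.9985 |

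The sample-size text quotes 1.5% and 82% where this rule gives 58.4% and 99.9%. At exactly 30 of 40 the lower limit of the exact two-sided 95% interval is 0.588, and the exact one-sided 98.5% lower bound is 0.571.

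**3. Sensitivity to response.** The documents give no dropout figure. If 30 to 39 of the 40 respond (an assumed range) and the rule is applied to respondents, the pass probability at a true 75% runs from 47% (24 of 31 needed) to 59% (24 of 32 needed).

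**4. Exact one-sided tests against 75%, n = 40.**

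| Passing count | Actual alpha at 75% | Power at 90% |
|---|---|---|
| 35 (87.5%) | 0.043 | 79% |
| 36 (90%) | 0.016 | 63% |
| 37 (92.5%) | 0.005 | 42% |

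Only 37 of 40 keeps alpha at or below 0.015. At 35 of 40 the one-sided 95% lower bound is 0.755, but the 98.5% bound is 0.716. Exact alpha of at most 0.015 with power of at least 82% first occurs at 63 in the intervention arm (55 of 63: alpha 0.0131, power 82.5%).

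**5. Denominator.** For illustration, assume 6 missing month-3 ratings and 26 satisfied. Then 26/34 = 76% meets the threshold and 26/40 = 65% does not.

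**The case against.** The best defence is that this is a 60-person pilot and 75% is a descriptive benchmark, read alongside the interviews. That is a legitimate design. However, the sample-size rationale attaches power and an alpha to the benchmark, and a purely descriptive threshold has neither.

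A second defence is that a true rate of exactly 75% satisfies a threshold of at least 75%, so passing there is no mistake. That stands under section 5.1. The 58% is an error rate only under the sample-size rationale, which puts 75% or less on the side to be distinguished from 90%. Below 75%, a pass is wrong on either reading, and it occurs 31% of the time at 70%.

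Four stronger readings are tempting, and the documents do not support them:

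- A reader might infer that the threshold decides whether the R01 trial goes ahead. The synopsis says the findings will lead to an application but sets no condition on 75%, and section 10.2 draws on interviews as well as the tabulation.
- A reader might infer from the sample-size sentence that 90% is the null and the burden of proof is reversed. The sentence names no null, and its 82% is reproduced only with 75% as reference and 90% as truth. Loose wording is the likelier explanation.
- A reader might infer that the power is 42% rather than 82%, because P(29 or fewer of 40) at a true 75% is 0.416. That compares the chance of failing at 75% with a figure that reproduces as the chance of passing at 90%. On the latter scale the threshold rule gives 99.9%. Its weakness is uncontrolled alpha. (The 42% power of the 37-of-40 test is a separate quantity.)
- A reader might infer that only returned surveys will be counted. The plan does not say so. It leaves missing ratings undefined.

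**Conclusion.** Wrong as written, and should be fixed. The plan quotes 82% power and a one-sided alpha of 0.015 for a primary outcome that it analyses by a rule with neither property. If all 40 respond, that rule passes with probability 58% at a true 75%, 31% at 70%, 12% at 65% and 99.9% at 90%. The conclusion rests on taking the threshold as applying to the tabulated proportion, which is the plain meaning where no test is named. It does not depend on full response: under the assumed 30 to 39 respondents, the figure at 75% stays between 47% and 59%. Because this is a pilot with no formal go/no-go rule, the defect lies in what the plan claims for its design. It does not invalidate the study.

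**What to change.** Make the synopsis (analysis plan and sample-size rationale), section 5.1 and section 10.2 state one rule, before any results are seen. There are two options:

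(a) Keep 75% as a descriptive benchmark. Delete the power and alpha claim from the sample-size rationale, and report the proportion with an exact 95% confidence interval.

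(b) Make it a test against 75% using an exact one-sided lower bound, and restate alpha and power in the sample-size rationale to match. Examples are at least 35 of 40 (alpha 0.043, power 79% at a true 90%), or at least 37 of 40 if 0.015 is kept (actual alpha 0.005, power 42%). At 36 of 40 alpha is 0.016, just over the stated level, with power 63%. Adopting 35 of 40 while leaving 0.015 in the rationale would create a new mismatch.

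Under either option, use everyone randomised to intervention as the denominator, which matches the 40 in the rationale. Count a missing month-3 rating as not satisfied, and show respondents only as a sensitivity analysis. If the number randomised to intervention is not 40, recompute the passing count. Under (b), missing ratings would lower the power figures above, which assume that 90% of all those randomised report satisfaction.

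The cost is a text amendment, with no change to visits, procedures or recruitment. Option (a) gives up the power statement. Option (b) sets a stricter bar than 30 of 40, with a less favourable stated power.
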